6.2.2.1.3 Rules for Withholding or Restarting

Tarlatamab should be withheld for any of the following:

- DLT
- Symptomatic hypophysitis (See Section 6.8.3)
- Criteria for conditional withholding of tarlatamab due to potential hepatotoxicity (Section 6.2.3)

Tarlatamab dosing can be resumed if the toxicities resolve to grade ≤ 1 or return to subjects' baseline values within 4 weeks. The restarting of therapy should be deemed safe by the investigator and medical monitor.

Subjects should not be restarted with tarlatamab if the following treatment-related adverse events occur:

- Any grade ≥ 4 adverse events except those not considered DLT as described in Section 6.2.1.2.2
- Grade 3 adverse event(s) that do not recover to Grade 0-1 within 4 weeks
- Any grade 3 adverse events that recur (with the exception of grade 3 laboratory parameters not considered clinically relevant or recurrent non-febrile grade 3 neutropenia which resolves with supportive care to grade ≤ 1 or returns to subjects' baseline values within 4 weeks)
- Criteria for permanent withholding of tarlatamab due to potential hepatotoxicity (Section 6.2.3)

For adverse events related to CRS, neurological events and pituitary dysfunction, please see Sections 6.8.1, 6.8.2, and 6.8.3 respectively for guidelines for withholding and restarting criteria to pause enrollment.

At any point during the study, enrollment will be paused at the occurrence of 2 or more Grade 4 or one or more Grade 5 IP related adverse events. DLRT will be reconvened to review the safety data and determine appropriate next step that may include but not limited to implementing safety/toxicity management, informing health authorities, voluntarily putting the clinical trial on hold, or proceeding with enrollment (note: following the occurrence of an enrollment pause and DLRT review, a subsequent enrollment pause will occur at the occurrence of 2 or more new Grade 4 or one or more Grade 5 IP

related adverse events; additionally, if a pause and a DLRT has already occurred and the appropriate safety/toxicity management for Grade 4 adverse events have already been implemented a subsequent enrollment pause may not occur).

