Table 9-2 Operating Characteristics with Batch Size of 10 Subjects

True Grade 4 or Higher Treatment-related Adverse Event Rate	Probability of Early Stopping of Dose Expansion	Average Dose Expansion Sample Size
0.10	2.0%	39.5
0.15	9.7%	37.6
0.20	25.8%	33.9
0.25	47.7%	28.8
0.30	69.2%	23.4

Interim futility analyses (non-binding) will be performed in a continuous manner using Bayesian predictive probability (Lee & Liu, 2008). Interim futility analyses in Part 2 will begin after approximately 20 subjects have been treated and has a minimum potential follow-up of 9 weeks. Interim futility analyses will be based on the ORR analysis set. Following this initial interim futility analysis, subsequent interim futility analyses will be performed after every 10 subjects in Part 2 have reached the data cutoff criteria, until all subjects are enrolled and evaluated. For interim futility analyses a response is defined as either a confirmed or unconfirmed CR or PR per RECIST 1.1. For the final analysis, a response is defined as a confirmed CR or PR per RECIST 1.1.

The Target Value (TV) is set to demonstrate a 18% increase in ORR (ie, TV = 30%) over the benchmark 12% ORR. For Part 2, at final analysis:

- NoGo criteria will be met if the probability that the true ORR exceeds the pre-specified TV of 30% is less than 5% (ie, NoGo: $P[\text{ORR} > \text{TV}] < 5\%$).

Given the existing observed data during the continuous monitoring stage, the Bayesian predictive probability is obtained by calculating the probability of reaching a NoGo decision should the treatment group be enrolled and evaluated to the maximum planned final sample size of 40 in Part 2. Further enrollment may be terminated if futility criteria are met. Notice the NoGo criteria is for interim futility analysis purpose only.

- Futility is met if it is predicted that there is a high probability of reaching a NoGo decision upon full enrollment of 40 subjects in Part 2 given the existing observed data (ie, predictive probability of a NoGo decision $> 95\%$).

The decision matrix for continuous monitoring of ORR is provided in [Figure 9-1](#) assuming a prior distribution of Beta (1, 1). For example, given TV of 30%, 3 or fewer observed responders after 30 subjects have reached the data cutoff criteria would trigger stopping enrollment claiming futility due to a high probability of reaching a NoGo decision upon full enrollment to 40 subjects given the existing observed data.

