All available study data, including demographics, investigational product (IP) administration, medical history, concomitant medications, adverse events, ECGs, vital signs, laboratory data, and PK/pharmacodynamic information will be reviewed. In addition to dose limiting toxicities (DLTs), all \geq grade 3 toxicities not meeting DLT criteria

will be reviewed and may be considered in DLRT recommendations. Data will not need to be source data verified and queries will not need to be resolved prior to the DLRM.

In the expansion phase, all available study data will be reviewed (with recruitment ongoing) by the DLRT after 10 and 20 subjects have at least completed their first treatment cycle plus two weeks or dropped out of treatment /study, whichever occurs earlier. Enrollment in dose expansion may continue while the DLRM preparation and meeting are in progress. Ad hoc meetings may be convened any time in case of important safety events.

Regulatory and Ethical Considerations

This study will be conducted in accordance with the protocol and with:

- Consensus ethical principles derived from international guidelines including the Declaration of Helsinki and Council for International Organizations of Medical Sciences International Ethical Guidelines
- Applicable International Council for Harmonisation (ICH) Good Clinical Practice (GCP) Guidelines
- Applicable ICH laws and regulations

The protocol, protocol amendments, informed consent form (ICF), Investigator's Brochure (IB), and other relevant documents (eg, subject recruitment advertisements) must be submitted to an **external review body (eg, IRB/IEC/regulatory authorities)** by the investigator and reviewed and approved by the **external review body**. A copy of the written approval of the protocol and ICF must be received by Amgen before recruitment of subjects into the study and shipment of Amgen investigational product.

Amgen may amend the protocol at any time. The investigator must submit and, where necessary, obtain approval from the **external review body** for all subsequent protocol amendments and changes to the informed consent document. The investigator must send a copy of the approval letter from the **external review body** and amended protocol Investigator's Signature page to Amgen prior to implementation of the protocol amendment at their site.

The investigator will be responsible for the following:

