7.1 Interim Analysis and Early Stopping Guidelines

Safety data will be reviewed on an ongoing basis. During dose exploration and formally during DLRMs, Amgen, in consultation with the site investigators, will review all available cumulative data by dose level prior to making dose escalation or dose de-escalation recommendations. Adverse events and DLTs observed in all subjects will be evaluated continually and fully integrated into all DLRMs and considered in all enrollment and dosing decisions.

For DLRMs, data will be subject to ongoing checks for integrity, completeness and accuracy; however, there is no requirement to resolve outstanding data issues ahead of the snapshot. All available data up to and including the data cut-off date will be included in the analysis based on an "as-is" snapshot of the database without data locking.

During dose expansion, Amgen will conduct evaluations of the ongoing grade 4 or higher treatment-related adverse event rate to assess if the threshold for possible early trial termination has been reached. If this threshold is met in either group in Part 2, enrollment to both dose expansion groups will be halted pending review of safety data by the DLRT. After receiving the DLRT recommendation, Amgen will choose to take one of the following actions.

- 1) Terminate the trial
- 2) Resume Dose Exploration with a schedule as outlined in the protocol and recommended by the DLRT.
- 3) Amend the protocol to potentially improve the benefit/risk for subjects (e.g., increase safety monitoring, modify dose/schedule, mandate premedication)
- 4) Continue dose expansion without any changes.

Date: 24 March 2023 Page 28 of 53

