The stopping rules use a Bayesian approach proposed by Thall and colleagues (Thall et al, 1995) to terminate the study if the posterior probability that the grade 4 or higher treatment-related adverse event rate is greater than 20% is > 80%. The stopping boundaries assume a prior distribution of Beta (0.40, 1.60) as presented in Table 7-1 and the operating characteristics with pre-specified batch size of 10 new subjects per batch are presented in Table 7-2. The operating characteristics in Table 7-2 provide the probability of stopping the trial early for given hypothetical true rate of grade 4 or higher treatment-related adverse events, whereas the stopping criteria in Table 7-1 are based on situations where the empirical evidence would result in a posterior probability of \geq 80% that the true grade 4 or higher treatment-related adverse event rate is \geq 20%.

Table 7-1. Stopping Boundary with Posterior Probability of 80% and Grade 4 or Higher Treatment-related Adverse Event Limit of 20%

Number of Subjects	Stop Subjects if Observing This Many Grade 4 or Higher Treatment-related Adverse Events
10	≥ 4
20	≥ 6
30	≥ 9
40	≥ 11
50	≥ 13
60	≥ 15
70	≥ 18
80	Dose Expansion Complete

Table 7-2. Operating Characteristics with Batch Size of 10 Subjects

True Grade 4 or Higher Treatment-related Adverse Event Rate	Probability of Early Stopping of Dose Expansion	Average Dose Expansion Sample Size
0.10	2.0%	78.6
0.15	11.9%	73.1
0.20	37.2%	60.3
0.25	69.8%	43.3

Date: 24 March 2023 Page 29 of 53

0.30	91.0%	29.1
------	-------	------

Interim futility analyses (non-binding) will be performed in a continuous manner using Bayesian predictive probability (Lee & Liu, 2008). Interim futility analyses will begin in each group after approximately 20 subjects have been treated and have a minimum potential follow-up of 9 weeks. Interim futility analyses will be based on the Interim Efficacy Analysis Set. Following this initial interim futility analysis, subsequent interim futility analyses will be performed after every 10 subjects in each group have reached the data cutoff criteria, until all subjects are enrolled and evaluated.

An additional interim analysis will be performed once each subject in this group either completes at least 6 months on study or withdraws from the study. For interim analyses a response is defined as either a confirmed or unconfirmed CR or PR as per RECIST 1.1. For the final analysis, a response is defined as a confirmed CR or PR as per RECIST 1.1.

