For the interim analysis, data will be subject to ongoing checks for integrity, completeness and accuracy with the expectation that outstanding data issues for selected CRF pages as deemed critical by the study team are resolved ahead of the snapshot to the extent possible. All available data up to and including the data cut-off date will be included in the analysis based on an "as-is" snapshot of the database with targeted data cleaning without data locking.

The Target Value (TV) is set to demonstrate a 18% increase in ORR (i.e., TV = 30%) over the benchmark 12% ORR. For Part 2, at final analysis:

 NoGo criteria will be met if the probability that the true ORR exceeds the pre-specified TV of 30% is less than 5% (i.e., NoGo: P[ORR > TV] < 5%).

Given the existing observed data during the continuous monitoring stage, the Bayesian predictive probability is obtained by calculating the probability of reaching a NoGo decision should the treatment group be enrolled and evaluated to the maximum planned final sample size of 40 in each group in Part 2. Further enrollment to the respective group in Part 2 may be terminated if futility criteria are met. Notice the NoGo criteria is for interim futility analysis purpose only.

 Futility is met if it is predicted that there is a high probability of reaching a NoGo decision upon full enrollment of 40 subjects in the respective group in Part 2

Date: 24 March 2023 Page 30 of 53

given the existing observed data (ie, predictive probability of a NoGo decision > 95%).

The decision matrix for continuous monitoring of ORR is provided in Figure 7-1 assuming a prior distribution of Beta (1, 1). For example, given TV of 30%, 3 or fewer observed responders after 30 subjects have reached the data cutoff criteria would trigger stopping enrollment claiming futility due to a high probability of reaching a NoGo decision upon full enrollment to 40 subjects in the respective group, given the existing observed data in that group.

Figure 7-1. Decision Matrix for Continuous Monitoring of ORR

Operating characteristics of this continuous monitoring method are presented in Table 7-3 and are based on 100 000 simulations using the prespecified TV value, and NoGo and Futility definitions.

A false NoGo is defined as observing either futility criteria during the continuous monitoring stage or NoGo criteria at final analysis when the true ORR is greater than or equal to the TV (ie, False NoGo: P[Futility or NoGo Decision | True ORR ≥ TV]).

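### SAP 7.1 halts Part 2 if either group of 40 meets the grade 4 or higher safety threshold, but Tables 7-1 and 7-2 are built for one pooled stream of 80

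*SAP*

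**What the plan says.** SAP 7.1 sets the threshold as a posterior probability above 80% that the grade 4 or higher treatment-related adverse event rate exceeds 20%, with a Beta(0.40, 1.60) prior. On the level at which it applies, the SAP says "If this threshold is met in either group in Part 2, enrollment to both dose expansion groups will be halted", pending review by the dose level review team (DLRT). The futility text in the same section refers to a "maximum planned final sample size of 40 in each group in Part 2", and SAP 3.2 gives about 80 subjects for Part 2.

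The "operating characteristics with pre-specified batch size of 10 new subjects per batch are presented in Table 7-2". Table 7-1 runs one subject count through 10, 20, 30, 40, 50, 60 and 70 and declares dose expansion complete at 80. Table 7-2 gives halt probabilities of 2.0/11.9/37.2/69.8/91.0% at true rates of 10/15/20/25/30%, with average sample sizes from 78.6 down to 29.1. Nothing legible says whether the counts are pooled across groups.

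The SAP is written for protocol Amendment 6. The supplied protocol (Amendment 7) has a single 40-subject expansion, no either-group wording, and its own Tables 9-1 and 9-2 for that size.

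**The concern.** Rows 50, 60 and 70 of Table 7-1 cannot be reached in a group of 40, and an average sample size of 78.6 cannot describe one group. The safety tables therefore count Part 2 as a whole, while the rule above them counts each group. Table 7-3, for futility in the same section, is on a 40-subject scale, so the section mixes the two levels.

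Two things are at stake. Table 7-2 is offered as the probability of stopping early and is read mainly for false alarms at rates at or below the 20% limit; it does not give those figures for the rule as worded. And a team applying the SAP cannot tell which count governs, although the two counts can give different answers on the same data.

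**Working it through.** **Inputs.** Criterion, prior and batches of 10: SAP 7.1. Group size 40: SAP 7.1, futility text. Part 2 total of about 80: SAP 3.2. Assumptions not in the documents: the groups are independent with a common true rate. SAP 7.1 gives no per-group schedule of safety looks. The main case takes looks at 10, 20 and 30, as in protocol Table 9-1, where reaching 40 is completion. A second case adds the 40-subject row printed in SAP Table 7-1.

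**1. Boundaries.** The smallest x with Pr(rate > 0.20 | Beta(0.4 + x, 1.6 + n − x)) > 0.80 is 4, 6, 9, 11, 13, 15, 18 at n = 10 to 70. All seven rows of Table 7-1 reproduce.

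**2. Table 7-2 as one stream of 80.** Exact binomial recursion with looks at 10 to 70 gives 2.1/11.9/37.2/69.8/91.0% and average N 78.6/73.1/60.3/43.3/29.1. This is Table 7-2, apart from 0.1 point in the first entry.

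**3. One group of 40, looks at 10, 20, 30.** The recursion gives 2.05/9.73/25.79/47.73/69.20%. Protocol Table 9-2 prints 2.0/9.7/25.8/47.7/69.2%.

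**4. Either of two groups.** Pr(halt) = 1 − (1 − p)², where p is the one-group probability. From the printed Table 9-2 value at a true rate of 20%: 1 − (1 − 0.258)² = 1 − 0.742² = 1 − 0.551 = 0.449. A simulation of 400,000 trials per rate agrees with the exact results.

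**5. Adding the 40-subject row (11 or more) in each group.** One group: 2.10/10.54/29.49/55.30/78.12%. At 20%: 1 − (1 − 0.2949)² = 1 − 0.497 = 0.503.

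| True rate | Table 7-2 | Either group, looks 10/20/30 | Difference (points) | Either group, with 40-subject row | Difference (points) |
|---|---|---|---|---|---|
| 10% | 2.0% | 4.1% | +2.1 | 4.2% | +2.2 |
| 15% | 11.9% | 18.5% | +6.6 | 20.0% | +8.1 |
| 20% | 37.2% | 44.9% | +7.7 | 50.3% | +13.1 |
| 25% | 69.8% | 72.7% | +2.9 | 80.0% | +10.2 |
| 30% | 91.0% | 90.5% | −0.5 | 95.2% | +4.2 |

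If only a group that finishes while the other still enrols has the look at 40, the figures lie between: 4.1/19.2/47.7/76.6/93.3%.

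**6. Average total N, looks at 10/20/30.** Groups enrolling in step: 77.9/70.9/58.3/44.2/33.3. One group after the other: 78.1/71.6/59.0/43.8/30.6. The largest gap from Table 7-2 is 33.3 − 29.1 = 4.2 subjects.

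**7. Same data, different answer.**
- 4/10 and 1/10: the first group crosses (posterior 0.895); pooled 5/20 does not (0.666).
- 3/10 and 3/10: neither group crosses (0.72 each); pooled 6/20 does (0.826).

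**8. The protocol's other pause.** Protocol 6.2.2.1.3 states that "enrollment will be paused at the occurrence of 2 or more Grade 4 or one or more Grade 5 IP related adverse events". Counting at most one grade 4 or higher related event per subject, the chance of two or more affected subjects at a true rate of 20% is 1 − 0.8¹⁰ − 10 × 0.2 × 0.8⁹ = 62.4% by 10 subjects, and 93.1% by 20. Both examples in step 7 would already have met this pause.

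**The case against.** The strongest reply is that this is version lag. The SAP implements Amendment 6, and the current protocol has one expansion of 40 with tables that fit it. That may prove to be the whole answer, but it cannot be assumed: the Amendment 6 summary adds a second cohort of about 40, and the Amendment 7 list of main changes does not mention removing it. The conflict also lies inside SAP 7.1, under the two-group design that the SAP itself describes.

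Second, text defining the groups is redacted in SAP 3.1 and 3.2, and apparently near Table 7-2. This limits what can be said about intent. It does not remove the conflict, because the rule, the group size and both tables are legible.

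Third, the practical effect is small. This stands. A crossing leads to DLRT review, and "Continue dose expansion without any changes" is a listed outcome. Under protocol Appendix 3, "all available study data will be reviewed (with recruitment ongoing) by the DLRT after 10 and 20 subjects". The pause in 6.2.2.1.3 usually comes first. The table-based halt matters mainly later, since that section adds that once toxicity management is in place "a subsequent enrollment pause may not occur".

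A reader might go further in three ways that the documents do not support:
- That Table 7-2 is miscalculated. It is correct for pooled counting, and Table 7-1 also runs to 80, so the element out of line may be the either-group phrase.
- That the 30% row is unaffected. This holds only if there is no look at 40.
- That patients are less protected. At equal rates the worded rule halts more often, or within 0.5 point as often.

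With unequal rates the sign depends on accrual order. At 30% and 10%, the either-group rule halts 69.8% of the time. Pooled counting halts 36.0% with five from each group per batch, 78.8% with the 30% group first and 10.6% with it last. These figures are illustration only, because Table 7-2 makes no claim about unequal rates.

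**Conclusion.** The point holds as a conflict between the wording of the safety rule and both of its tables; the legible text does not show which was meant. Read as worded, the halt probability at a true rate of 10% is about double the stated 2.0%. At 20% it is 7.7 points above the stated 37.2%, or 13.1 points with a look at 40. These sizes assume independent groups of 40 and a common true rate. The per-group look schedule is also an assumption, so there is no single as-worded figure. No endpoint or estimate is affected. It should be corrected, because the stated operating characteristics do not belong to the rule and the governing count is undefined.

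**What to change.** First confirm whether the two-group Part 2 still applies.

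If it does not, align SAP 3.2 and 7.1 with the protocol's single 40-subject expansion, remove the either-group wording, and use protocol Tables 9-1 and 9-2.

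If it does, choose one:
- **(a) Per-group monitoring.** State the looks in each group, including whether there is one at 40. End Table 7-1 at the last of them. Recompute Table 7-2 as either-group operating characteristics, stating the independence, common-rate and accrual assumptions.
- **(b) Pooled monitoring.** State that counts are pooled across Part 2, replace the either-group phrase, and keep both tables.

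A sentence relating this rule to the enrollment pause in protocol 6.2.2.1.3 would help but is optional.

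The cost is SAP text only: about one sentence under (b), and a shortened Table 7-1 with a recomputed Table 7-2 under (a). No additional subjects are needed.

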7.2 Primary Analysis

The primary analysis will be performed when target enrollment is complete and each subject either completes at least 6 months on study or withdraws from the study.

For the primary analysis, data will be subject to ongoing checks for integrity, completeness and accuracy with the expectation that outstanding data issues are resolved ahead of the lock. The data supporting the interim analysis will be locked to prevent further changes.

7.3 Final Analysis

The final analysis will be performed after the last subject has had an opportunity to complete the corresponding end of treatment (EOT) visit/procedures.

For the final analysis, data will be subject to ongoing checks for integrity, completeness and accuracy with the expectation that all outstanding data issues are resolved ahead of the final lock.

8. Data Screening and Acceptance

8.1 General Principles

The objective of the data screening is to assess the quantity, quality, and statistical characteristics of the data relative to the requirements of the planned analyses.

8.2 Data Handling and Electronic Transfer of Data

The Amgen Global Study Operations-Data Management (GSO-DM) department will provide all data to be used in the planned analyses. This study will use the RAVE database.

8.3 Handling of Missing and Incomplete Data

Partially missing adverse event, concomitant medication and death dates will be imputed as outlined in Appendix A.

8.4 Detection of Bias

Lack of protocol compliance and the potential for biased statistical analyses will be examined by assessing the incidence of important protocol deviations in each study part. The clinical study team will identify and document the criteria for important protocol deviations.

Date: 24 March 2023 Page 32 of 53

